4.6.5.1. Abnormal Hepatic Tests

Analyses for abnormal hepatic tests involve 4 laboratory analytes: ALT, AST, total bilirubin, and ALP. Analyses for the change from baseline to last visit that occurred on or before the date of treatment discontinuation and shift tables are described in Section 4.6.5. This section describes additional analyses for the topic. The central laboratory reference ranges (Labcorp) will be used for ALT, AST, total bilirubin, and ALP hepatic laboratory assessments.

The number and percentage of patients with the following abnormal elevations in hepatic laboratory tests at any time up to 60 days after treatment discontinuation will be summarized by treatment group. LY3471851 groups will be compared to placebo using Fisher's exact test:

- The percentages of patients with an ALT measurement $\geq 3\times$, $5\times$, and $10\times$ the central laboratory upper limit of normal (ULN) during the treatment and follow-up periods will be summarized for all patients with a postbaseline value.
- The percentages of patients with an AST measurement $\geq 3\times$, $5\times$, and $10\times$ the central laboratory ULN during the treatment and follow-up periods will be summarized for all patients with a postbaseline value.
- The percentages of patients with a total bilirubin measurement $\geq 2 \times$ the central laboratory ULN during the treatment period will be summarized for all patients with a postbaseline value.
- The percentages of patients with an ALP measurement $\geq 3\times$ the central laboratory ULN during the treatment and follow-up periods will be summarized for all patients with a postbaseline value.

Second, to further evaluate potential hepatotoxicity, an Evaluation of Drug-Induced Serious Hepatotoxicity (eDISH) plot will be created for all patients whether treated with LY3471851 and/or other treatment using the whole study and follow-up periods. Each patient with at least 1 postbaseline ALT and total bilirubin will be included in the eDISH. The points correspond to maximum total bilirubin and maximum ALT, even if not obtained from the same blood draw. A listing of patients potentially meeting Hy's rule will be provided (defined as greater than or equal to 3× ULN for ALT or AST, and greater than or equal to 2× ULN for total bilirubin, not necessarily at the same time).

Third, a listing will be provided to the medical safety team for internal review according to the following SMQs:

- Broad and narrow terms in the Liver-related investigations, signs and symptoms SMQ (SMQ 20000008)
- Broad and narrow terms in the Cholestasis and jaundice of hepatic origin SMQ (SMQ 20000009)
- Broad and narrow terms in the Hepatitis non-infectious SMQ (SMQ 20000010)
- Broad and narrow terms in the Hepatic failure, fibrosis and cirrhosis and other liver damage-related conditions SMQ (SMQ 20000013)
- Narrow terms in the Liver-related coagulation and bleeding disturbances SMQ (SMQ 20000015).

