In addition, based on observations of treatment-related biliary hyperplasia noted in nonclinical studies, as described in the IB, investigators should be aware of the possible occurrence of treatment-related hepatobiliary changes that could possibly include cholestasis. The protocol includes hepatic-related laboratory testing to support intensive monitoring for symptoms and physical signs suggestive of liver or biliary toxicity, including jaundice, scleral icterus, and pruritis (see Section 8.2.9).

Ongoing study-level monitoring of safety data will be performed, as described in Section 8.2. Interim analyses to review unblinded safety data will also be conducted, as described in Section 9.5 and Section 10.1.5.

The efficacy of LY3471851 in UC has not been established. Participants may benefit by receiving personal health information from the physical examinations and from other routine safety assessments performed in this study.

More detailed information about the known and expected benefits and risks and reasonably expected adverse events of LY3471851 may be found in the IB.

3. Objectives and Endpoints

This table shows the objectives, endpoints, and estimands of the study. Primary and secondary efficacy endpoint definitions appear in Section 8.1.

Objectives	Estimands/Endpoints
Primary	

 To determine whether LY3471851 is superior to placebo in inducing clinical remission in participants with moderately to severely active UC 	
The study will compare LY3471851 with placebo in participants with moderately to severely active UC.
 
The primary comparison of interest is the difference in the proportion of participants who achieve clinical remission at Week 12.
 
The primary comparison will be assessed using a composite estimand where the intercurrent events that lead to permanent discontinuation of assigned study treatment are part of the response definition.

Secondary	

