- Box plots for observed values: Values at each visit (starting at randomization) and change from baseline to each visit and to last postbaseline measure will be displayed in box plots for patients who have a baseline and at least 1 postbaseline visit. For visits included in the treatment period, patients will be included only if the visit occurs on or before the date of treatment discontinuation/completion. Follow-up visit will be the first visit that occurred during the Follow-up period. Individual measurements outside of reference limits will also be displayed using distinct symbols overlaying the box plot. Original-scale data will be used for the display but for some analytes (e.g., immunoglobulins) a logarithmic scale will be used to aid in viewing the measures of central tendency and dispersion. Unplanned measurements will be excluded. Descriptive summary statistics will be included in a table below the box plot. These box plots will be

used to evaluate trends over time and to assess a potential impact of outliers on central tendency summaries. A p-value for change from baseline to endpoint will be provided using an ANCOVA model with explanatory term for treatment and the baseline value as a covariate. Endpoint will be the last observation where patient is on treatment.

- Treatment-emergent high/low analyses: The number and percentage of patients with treatment-emergent high and low laboratory results at any time will be summarized by treatment group. Planned and unplanned measurements will be included. A treatment-emergent **high** result is defined as a change from a value less than or equal to the high limit at all baseline visits to a value greater than the high limit at any time during the treatment period and up to 60 days after treatment discontinuation. A treatment-emergent **low** result is defined as a change from a value greater than or equal to the low limit at all baseline visits to a value less than the low limit at any time during the treatment period and up to 60 days after treatment discontinuation. The Fisher's exact test will be used for the treatment comparisons.

For laboratory analyte measurements collected qualitatively, a listing of abnormal findings will be created. The listing will include patient ID, treatment group, laboratory collection date, analyte name, and analyte finding.

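### The bilirubin row of the SAP hepatic table ends with treatment, against its own lead-in and the ALT, AST and ALP rows, so values of at least 2×ULN first seen after drug stop may be left out of that by-arm comparison

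*SAP*

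**What the plan says.** SAP 4.6.5.1 introduces a list of four hepatic tests and says that "abnormal elevations in hepatic laboratory tests at any time up to 60 days after treatment discontinuation will be summarized by treatment group", with each LY3471851 group compared with placebo by Fisher's exact test. The rows then set their own windows:

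- ALT (3×, 5×, 10×ULN): "the central laboratory upper limit of normal (ULN) during the treatment and follow-up periods will be summarized for all patients with a postbaseline value".
- AST (3×, 5×, 10×ULN) and ALP (3×ULN): "the central laboratory ULN during the treatment and follow-up periods will be summarized".
- Total bilirubin (2×ULN): "the central laboratory ULN during the treatment period will be summarized".

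The general laboratory section, SAP 4.6.5, has a separate treatment-emergent high analysis. For participants within range throughout baseline, it counts a change "to a value greater than the high limit at any time during the treatment period and up to 60 days after treatment discontinuation", by treatment group and with Fisher's exact test. SAP Appendix 10 marks total bilirubin for outlier/shift analysis.

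Protocol 2.3 alerts investigators to "treatment-related hepatobiliary changes that could possibly include cholestasis", on the basis of nonclinical biliary findings.

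**The concern.** One list gives three descriptions of its time window, and bilirubin alone is cut off at the end of treatment. A programmer cannot satisfy both the lead-in and the bilirubin row, and the SAP does not say which governs.

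If the row governs, a participant whose bilirubin first reaches 2×ULN after stopping drug drops out of the bilirubin count. The same blood sample can still count for ALT, AST or ALP.

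The threshold matters here. Protocol 8.2.9 and 8.2.9.1 use total bilirubin of at least 2×ULN as a trigger for repeat testing, comprehensive evaluation and extra hepatic data collection (Gilbert's syndrome excepted). Bilirubin is also a natural marker for the cholestatic risk named in Protocol 2.3. Participants who stop because of a liver abnormality have their repeat samples and follow-up visits after drug stop, and a row that ends with treatment does not look there.

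**Working it through.** The SAP gives no figure to reproduce. The check compares the windows and works out which scheduled samples fall in each.

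**Are the data collected?** Yes. Table 4 of the protocol's schedule of activities has clinical chemistry at the early termination visit, Visit 801 and Visit 802. Protocol Appendix 2 includes total bilirubin in that panel. Protocol 8.2.9 adds repeat tests after abnormal liver results.

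**Visit timing.** Table 2 of the schedule puts the last dose at Week 50 (Day 351) and Week 52 at Day 365. Table 4 puts Visit 801 at Week 58 and Visit 802 at Week 66 (anti-HBc-positive participants only), each ±7 days.

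- Visit 801: 58 × 7 + 1 = Day 407. From the last dose, 407 − 351 = 56 days, or 49 to 63 with the tolerance. From Week 52, 407 − 365 = 42 days, or 35 to 49.
- Visit 802: 66 × 7 + 1 = Day 463. From the last dose, 463 − 351 = 112 days, or 105 to 119. From Week 52, 463 − 365 = 98 days, or 91 to 105.

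**Which samples each wording admits:**

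| Wording | Visit 801 | Visit 802 |
|---|---|---|
| Lead-in (60 days after discontinuation) | In on schedule; out on days 61 to 63 if counted from the last dose | Out |
| ALT, AST, ALP rows (treatment and follow-up) | In | In |
| Bilirubin row (treatment only) | Out | Out |

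The bilirubin row therefore conflicts with both of the other wordings. Those two also conflict with each other, for every Visit 802 and for a Visit 801 more than 60 days after the last dose. If the 60 days run from Week 52 instead, Visit 801 is always inside and Visit 802 is still outside.

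**What other analyses recover after drug stop:**

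- *Treatment-emergent high (SAP 4.6.5):* by arm, tested, planned and unplanned samples, to 60 days. The threshold is the upper limit itself, so a small excursion and a value of 2×ULN count alike.
- *eDISH plot (SAP 4.6.5.1):* covers the whole study and follow-up, but is a plot of maximum bilirubin against maximum ALT, not a by-arm count.
- *Hy's rule listing (SAP 4.6.5.1):* no window is stated. It also requires ALT or AST of at least 3×ULN, so an isolated or cholestatic bilirubin rise does not qualify.
- *Liver-related SMQ listing (SAP 4.6.5.1):* depends on an adverse event having been reported.

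None of these gives a by-arm count and test at 2×ULN after drug stop.

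**The case against.** The strongest reply is that little is lost.

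- Inclusion Criterion 11 requires total bilirubin no higher than 1×ULN at screening, except in Gilbert's syndrome. Nearly every new rise to 2×ULN within 60 days of stopping therefore also enters the treatment-emergent high comparison.
- The liver-test conditions for considering discontinuation in Protocol 7.1.1 all require raised ALT, AST or ALP. A participant stopped on ALT or AST whose bilirubin later reaches 2×ULN meets the Hy's rule listing, which does not require the two at the same time. One stopped on ALP above 3×ULN is in the ALP row.
- By Visit 801, 56 / 13 = 4.3 to 56 / 8 = 7 half-lives have passed, using the 8 to 13 days in Protocol 4.2.
- If the lead-in governs, bilirubin within 60 days is included after all.

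Most of this stands, and it rules out stronger readings. A reader might infer that bilirubin rises after drug stop are not counted by arm at all, or that such a participant is treated as having normal bilirubin. SAP 4.6.5 shows otherwise: the participant is high in the treatment-emergent analysis if within range at baseline and within 60 days, and appears on the eDISH plot if ALT was also measured. A reader might also infer that the plan overlooks serious liver cases. The listings and the ALP row make that unsupported.

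The objection does not remove the contradiction in the text, and no other planned output supplies the by-arm comparison at 2×ULN after drug stop. The half-life argument applies to scheduled Visit 801, not to repeat samples taken soon after stopping.

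**Conclusion.** The point holds in narrow form. The bilirubin row contradicts its lead-in and differs from the other three rows without a stated reason. On its literal wording, values of at least 2×ULN first seen after drug stop are missing from the by-arm hepatic table and its Fisher's test at that threshold.

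This rests on the row taking precedence over the lead-in, which the SAP neither says nor rules out. It also takes Visits 801 and 802 as lying outside the treatment period, which the protocol's description of them as post-treatment follow-up supports. The number of participants affected cannot be derived from the documents. The primary and secondary efficacy analyses are untouched. It is a minor point, worth correcting because the risk is named in the protocol and the correction is almost free.

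**What to change.** In SAP 4.6.5.1, extend the total bilirubin row past drug stop and state one identical window for the lead-in and all four rows. Either choice is workable:

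- **60 days after treatment discontinuation.** This matches the treatment-emergent high analysis in SAP 4.6.5. It drops Visit 802 for all four tests, and the SAP should state the date from which the 60 days run, since that decides whether a late Visit 801 counts.
- **The whole follow-up period.** This matches the eDISH plot and keeps both visits. Anti-HBc-positive participants are then observed longer than the rest.

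Changing the bilirubin row alone would leave the mismatch between the lead-in and the other rows in place. The cost is a few words in the SAP and one window definition in the programming. No new data are needed. The change should be made before unblinding.

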10. Are on a stable dose, defined as listed here, if using these medications:
 - 10a. oral 5-ASA therapy: The prescribed dose has been stable for at least 2 weeks prior to the screening endoscopy.
 - 10b. oral corticosteroid therapy (prednisone ≤ 20 mg/day or equivalent, or budesonide extended release tablets 9 mg/day [budesonide MMX]): The prescribed dose has been stable for at least 2 weeks before the screening endoscopy.
 - 10c. AZA, 6-MP, and methotrexate: The prescribed dose has been stable for at least 8 weeks before the screening endoscopy.

Diagnostic Assessments

11. Have clinically acceptable central laboratory test results at screening (retesting is allowed for hematology and chemistry), as assessed by the investigator, including
 - 11a. hematology
 - absolute neutrophil count ≥ 1.5 times (x) $10^9/L$ ($\geq 1.5 \times 10^3/\mu L$ or ≥ 1.5 GI/L)
 - platelet count $\geq 100 \times 10^9/L$ ($\geq 100 \times 10^3/\mu L$ or ≥ 100 GI/L)
 - hemoglobin ≥ 8.5 g/dL (≥ 85 g/L) for males and > 8.0 g/dL (> 80 g/L) for females
 - lymphocyte count ≥ 500 cells/ μL ($> 0.50 \times 10^3/\mu L$ or > 0.50 GI/L), and
 - total white blood cell count $\geq 3.0 \times 10^9/L$ ($\geq 3.0 \times 10^3/\mu L$ or ≥ 3.0 GI/L)
 - 11b. chemistry
 - serum creatinine ≤ 1 times upper limit of normal (ULN)

- estimated glomerular filtration rate (eGFR) (Modification of Diet in Renal Disease [MDRD]) ≥ 60 mL/min/1.73 m²³⁶
- total bilirubin level (TBL) ≤ 1 times ULN
- alanine aminotransferase (ALT) and aspartate aminotransferase (AST) ≤ 1 times ULN
- alkaline phosphatase (ALP) ≤ 1 times ULN

Note: Patients with an established diagnosis of Gilbert's syndrome (requires source documentation showing unconjugated hyperbilirubinemia, with no evidence of hemolysis) can be included with bilirubin levels ≤ 3 times ULN.

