8.2.9. Hepatic Safety Monitoring

Close hepatic monitoring

The laboratory tests listed in Appendix 5, including ALT, AST, ALP, TBL, direct bilirubin, GGT, and CK, should be repeated within 48 to 72 hours to confirm the abnormality and to determine whether it is increasing or decreasing, if any of the conditions listed in this table occur.

If a participant has the following elevations:

ALT or AST ≥ 3 times ULN

ALP ≥ 2 times ULN

TBL ≥ 2 times ULN (except for patients with Gilbert's syndrome)

Abbreviations: ALP = alkaline phosphatase; ALT = alanine aminotransferase; AST = aspartate aminotransferase; TBL = total bilirubin level; ULN = upper limit of normal.

If the abnormality persists or worsens, clinical and laboratory monitoring, and evaluation for the possible causes of the abnormal liver tests should be initiated by the investigator in consultation with the sponsor's designated medical monitor. At a minimum, this evaluation should include a physical examination and a thorough medical history, including symptoms, recent illnesses (for example, heart failure, systemic infection, hypotension, or seizures), recent travel, history of concomitant medications (including over-the-counter), herbal and dietary supplements, history of alcohol drinking, and other substance abuse.

Initially, monitoring of symptoms and hepatic biochemical tests should be done at a frequency of 1 to 3 times weekly, based on the participant's clinical condition and hepatic biochemical tests. Subsequently, the frequency of monitoring may be lowered to once every 1 to 2 weeks, if the participant's clinical condition and lab results stabilize. Monitoring of ALT, AST, ALP, and TBL should continue until levels normalize or return to approximate baseline levels.

Comprehensive hepatic evaluation

A comprehensive evaluation should be performed to search for possible causes of liver injury, if 1 or more of the conditions listed in this table occur:

If a participant has the following elevations:

ALT or AST ≥ 3 times ULN with hepatic signs/symptoms^a, or
ALT or AST ≥ 5 times ULN

ALP ≥ 3 times ULN

TBL ≥ 2 times ULN (except for patients with Gilbert's syndrome)

Abbreviations: ALP = alkaline phosphatase; ALT = alanine aminotransferase; AST = aspartate aminotransferase; TBL = total bilirubin level; ULN = upper limit of normal.

^a **Hepatic signs/symptoms are severe fatigue, nausea, vomiting, right upper quadrant abdominal pain, fever, rash, and/or eosinophilia $>5\%$.**

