At a minimum, this evaluation should include a physical examination and a thorough medical history, as outlined above, as well as

- tests for prothrombin time (PT-INR)
- tests for viral hepatitis A, B, C, and E, and
- tests for autoimmune hepatitis, and an abdominal imaging study (for example, ultrasound or CT scan).

Based on the participant's history and initial results, further testing should be considered in consultation with the sponsor's designated medical monitor, including tests for

- hepatitis D virus (HDV)
- cytomegalovirus (CMV)
- Epstein-Barr virus (EBV)
- acetaminophen levels
- acetaminophen protein adducts
- urine toxicology screen

- Wilson's disease
- blood alcohol levels
- urinary ethyl glucuronide, and
- serum phosphatidylethanol.

Based on the circumstances and the investigator's assessment of the participant's clinical condition, the investigator should consider referring the participant for a

- hepatologist/gastroenterologist consultation
- magnetic resonance cholangiopancreatography (MRCP)
- endoscopic retrograde cholangiopancreatography (ERCP)
- cardiac echocardiogram, or
- liver biopsy.

8.2.9.1. Additional Hepatic Data Collection in Participants Who Have Abnormal Liver Tests During the Study

Additional hepatic safety data collection (hepatic safety eCRF) should be performed for participants who meet 1 or more of the following conditions:

- Elevation of serum ALT to ≥ 5 times ULN on 2 or more consecutive blood tests
- Elevated TBL to ≥ 2 times ULN (except for cases of known Gilbert's syndrome)
- Elevation of serum ALP to ≥ 2 times ULN on 2 or more consecutive blood tests
- Hepatic event considered to be an SAE.
- Discontinuation of study drug due to a hepatic event (Section 7.1).

Note: The interval between the 2 consecutive blood tests should be at least 2 days.

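### The SAP's bilirubin row counts any value of 2x ULN or more as an abnormal elevation, although participants with Gilbert's syndrome may enter at up to 3x ULN

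*SAP*

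**What the plan says.** **Entry.** Protocol 5.1, criterion 11b, requires total bilirubin, ALT, AST and ALP each to be no more than 1x ULN. Its note makes one exception: patients with documented Gilbert's syndrome "can be included with bilirubin levels" of up to 3x ULN. ALT, AST and ALP have no such exception.

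**Analysis.** SAP 4.6.5.1 introduces its hepatic table as "The number and percentage of patients with the following abnormal elevations in hepatic laboratory tests at any time up to 60 days after treatment discontinuation" and adds that "LY3471851 groups will be compared to placebo using Fisher's exact test". The bilirubin row counts participants at 2 or more times "the central laboratory ULN during the treatment period will be summarized for all patients with a postbaseline value". The listing of potential Hy's-rule cases requires ALT or AST of at least 3x ULN "and greater than or equal to 2× ULN for total bilirubin, not necessarily at the same time". The eDISH plot uses each participant's maximum bilirubin and maximum ALT as absolute values. None of the three refers to baseline bilirubin or to Gilbert's syndrome.

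**Protocol triggers at the same threshold.** In Protocol 8.2.9 the 2x ULN bilirubin trigger appears twice, for close monitoring and for comprehensive evaluation. Each time it applies "except for patients with" Gilbert's syndrome. In 8.2.9.1 the trigger for extra hepatic data collection applies "except for cases of known" Gilbert's syndrome.

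**The concern.** The event threshold (2x ULN) lies inside the permitted entry range (up to 3x ULN) for one subgroup, so a participant can be an event on the day of entry. Bilirubin is the only one of the four hepatic analytes with this problem. ALT, AST and ALP are capped at 1x ULN at entry and counted from 3x, so their rows need no baseline condition.

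Protocol 2.3 tells investigators to expect possible hepatobiliary changes, including cholestasis, and bilirubin is one of the main laboratory readouts for that risk. A row that mixes stable pre-existing hyperbilirubinemia with new elevations is harder to read, and arms are small enough that a single participant visibly moves the percentage.

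**Working it through.** **No planned figure to reproduce.** The documents give no expected count for this row. The check applies the written rules to participants who could be enrolled.

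**Rules applied (multiples of ULN)**
- Bilirubin row, SAP 4.6.5.1: postbaseline TBL of at least 2.
- Treatment-emergent high, SAP 4.6.5: TBL at or below the high limit at all baseline visits, then above it.
- Hy's-rule listing, SAP 4.6.5.1: ALT or AST of at least 3, and TBL of at least 2.

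| Participant | Bilirubin row | Treatment-emergent high | Hy's-rule listing |
|---|---|---|---|
| Gilbert's, TBL unchanged at 2.0, 2.5 or 3.0; ALT at most 1 | counted | no | no |
| Gilbert's, TBL unchanged at 1.5; ALT 0.8 | no | no | no |
| Gilbert's, TBL unchanged at 2.5; ALT new at 3.2 | counted | no | listed |
| Not Gilbert's, TBL unchanged at 1.0; ALT 1.0 | no | no | no |
| Not Gilbert's, TBL from 0.9 to 2.2; ALT 0.8 | counted | yes | no |

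If baseline TBL must be below 2, the first and third profiles leave the bilirubin row and the last one stays.

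**Weight of one participant.** This is 100/N percentage points. Stage 1 randomizes about 100 at 2:2:1, so placebo has about 20. Protocol 9.2 and SAP 5 assume 40, 60 or 80 per active arm and 40 on placebo.
- N = 20: 5.0 points
- N = 40: 2.5 points
- N = 60: 1.7 points
- N = 80: 1.25 points

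**Chance that an arm contains at least one.** Let q be the share of participants with Gilbert's and baseline TBL of 2x ULN or more. The documents give no value, so q is assumed. The chance is 1 - (1 - q)^N.

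| q (assumed) | N = 40 | N = 80 |
|---|---|---|
| 0.5% | 18% | 33% |
| 1% | 33% | 55% |
| 2% | 55% | 80% |
| 5% | 87% | 98% |

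**Fluctuation around 2x.** This is a simulation with no drug effect: log-normal bilirubin, a screening value of at most 3x, seven postbaseline draws (Visits 3 to 9), and an assumed within-person CV of 20-30%. The chance that a Gilbert's participant is counted at least once depends on the usual level:
- 1.2x: 3-19%
- 1.5x: 35-62%
- 1.8x: 88-92%
- 2.2x: over 99%

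With usual levels spread evenly over 1.0-2.5x and CV 25%, 66% are counted. About 60% of those had a single baseline draw below 2x. In the same setting, a baseline-below-2x condition on its own still counts about 26% of Gilbert's participants if both baseline draws must be below 2x, and about 38-40% if only one must be. A baseline condition alone is therefore not enough.

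**Effect on Fisher's exact test (two-sided).** Suppose an active arm has extra cases and placebo has 0 of 40. One case gives p = 1.0 at N = 40, 60 or 80. For two cases:
- N = 40: 2 x C(40,2)/C(80,2) = 2 x 780/3160 = 0.49.
- N = 80: [C(80,2) + C(40,2)]/C(120,2) = (3160 + 780)/7140 = 0.55.

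Two placebo cases against 0 of 80 give 780/7140 = 0.11. Reaching p below 0.05 against 0 of 40 takes 6 of 40, 7 of 60 or 9 of 80.

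**The case against.** The opposing case has five parts.

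1. **Hy's-rule listing.** A reader might infer that stable Gilbert's participants will be listed as potential Hy's-rule cases. They will not. ALT and AST must be at or below 1x ULN at entry, so a new transaminase rise to 3x or more is required. The output is also a listing of potential cases, open to individual review. This stands. What remains is that the unchanged bilirubin already meets the bilirubin half, and that on the eDISH plot the participant sits at or above 2x.

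2. **False signal.** A reader might infer that one or two such participants could produce a significant difference. The Fisher calculations do not support that, and randomization gives no expected imbalance in Gilbert's status. This stands. The harm is to the interpretation of the row.

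3. **Conflict with the protocol.** A reader might infer that the SAP contradicts the protocol. The exceptions in 8.2.9 and 8.2.9.1 govern retesting, work-up and data collection, not analysis tables. Protocol 7.1.1 combines ALT or AST above 3x with bilirubin above 2x and makes no Gilbert's exception, so the listing has a parallel in the protocol. This stands as a limit. The exceptions show that the protocol recognizes the issue at this threshold; they do not bind the SAP.

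4. **Size.** A reader might take the simulated 66% as the share of Gilbert's participants whose unchanged baseline is miscounted. Most of that figure is assumed fluctuation from below 2x, and the usual levels and CV are assumptions too. This stands.

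5. **Other analyses.** SAP 4.6.5 plans change from baseline with baseline as covariate, and treatment-emergent high results. SAP 6.10 includes direct bilirubin, and SAP 4.6.5.1 adds ALP at 3x and a review of cholestasis terms. These help a reader, but none governs the 2x row. The treatment-emergent rule cannot register any rise in a participant already above ULN at baseline, so it does not fill the gap for Gilbert's participants.

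**Conclusion.** The point holds for the bilirubin row of SAP 4.6.5.1. As written, an eligible Gilbert's participant who enters at 2-3x ULN and does not change is reported as having an abnormal elevation, and one entering just below 2x can be counted by ordinary variation. This follows from the text and needs no assumption about prevalence.

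Its size is modest: 2.5 percentage points per participant in an arm of 40 and 1.25 in an arm of 80. The number of such participants is not given and is probably small. The Hy's-rule listing and the eDISH plot are affected only in their bilirubin component. The change is worth making for clarity; the planned safety analysis is not invalid without it.

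**What to change.** In SAP 4.6.5.1:

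- Keep the existing all-patient row, so that nothing is hidden.
- Add a bilirubin row at 2x ULN or more that excludes participants with documented Gilbert's syndrome or with baseline total bilirubin of 2x ULN or more. State which baseline draws define this condition, since chemistry is taken at both Visit 1 and Visit 2.
- Report Gilbert's participants separately, relative to their own baseline, so that a real rise in them can still be seen.
- Flag Gilbert's participants on the eDISH plot and in the Hy's-rule listing, without removing them.

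The inputs already exist: baseline chemistry, medical history at Visit 1, and the source documentation that criterion 11b requires. The cost is one or two extra table rows and a programming flag. No clinical rule or data collection changes.
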